4. PARTICIPANT SELECTION

4.1 Inclusion Criteria

4.1.1 Participants with oral leukoplakia or erythroplakia with mild, moderate, or severe histologic dysplasia, or hyperplasia not associated with mechanical factors such as ill-fitted dentures.

4.1.2 Measurable disease – minimum lesion size of 8x3 mm before initial biopsy.

4.1.3 Age \geq 18 years.

4.1.4 Karnofsky performance status \geq 70%.

4.1.5 Participants must have normal organ and marrow function as defined below:

Leukocytes	\geq 3,000/microliter
Absolute neutrophil count	\geq 1,000/microliter
Platelets	\geq 100,000/microliter
Total bilirubin	\leq 1.5 \times institutional ULN
AST (SGOT)/ALT (SGPT)	\leq 1.5 \times institutional ULN

eGFR $>$ 40 mL/min using the Cockcroft-Gault equation
(<http://www.mdcalc.com/creatinine-clearance-cockcroft-gault-...equation/>).

4.1.6 Life expectancy $>$ 3 months.

4.1.7 Willing to use adequate contraception (barrier method, abstinence, subject has had a vasectomy or partner is using effective birth control or is postmenopausal) for the duration of study participation because the effects of metformin on the developing human fetus are unknown even though it is not teratogenic in rats and rabbits at 2-6 times the maximum recommended human daily dose.

4.1.8 Ability to take oral medication.

4.1.9 Ability to understand and the willingness to sign a written informed consent document.

4.2 Exclusion Criteria

4.2.1 Patients with diabetes who are taking insulin or oral agents.

4.2.2 History of diabetic ketoacidosis.

4.2.3 Participants may not be receiving any other investigational agents within past 3 months.

- 4.2.4 History of allergic reactions attributed to compounds of similar chemical composition to metformin or prior use of metformin within the last year.
- 4.2.5 Uncontrolled intercurrent illness including, but not limited to, ongoing or active infection, HIV-positive, symptomatic congestive heart failure, unstable angina pectoris, cardiac arrhythmia, or psychiatric illness/social situations that would limit compliance with study requirements.
- 4.2.6 Oral carcinoma in situ.
- 4.2.7 History of chronic alcohol use or abuse defined as any one of the following: a) average consumption of 3 or more alcohol containing beverages daily in the past 12 months; b) consumption of 7 or more alcoholic beverages within a 24 hr period in the past 12 months.
- 4.2.8 HbA1c > 8%.
- 4.2.9 Pregnancy or nursing women.
- 4.2.10 Acute or chronic liver disease, evidence of hepatitis (infectious or autoimmune), cirrhosis or portal hypertension.
- 4.2.11 History of renal disease.
- 4.2.12 History of prior HNSCC unless curatively treated for ≥ 1 year.
- 4.2.13 Have received chemotherapy and/or radiation for any malignancy (excluding non-melanoma skin cancer and cancers confined to organs with removal as only treatment) in the past 2 years. Ongoing adjuvant hormonal therapy for breast cancer is allowed.

4.3 Inclusion of Women and Minorities

Both men and women and members of all races and ethnic groups are eligible for this trial.

4.4 Recruitment and Retention Plan

Individuals with oral leukoplakia or erythroplakia will be recruited from local hospitals, Veterans Administration hospitals, pathology services, dental schools, dentist networks, and from advertising in local media.

The study team will provide a friendly and comfortable study setting for participants from initial contact through the completion of their study activities. Demands upon the subjects will be minimized to foster comfort while preserving the research goals. Wherever possible, flexibility will be built into the study schedule to promote compliance.

5. AGENT ADMINISTRATION

Intervention will be administered on an outpatient basis. Reported adverse events (AEs) and potential risks are described in Section 6.2.

5.1 Dose Regimen and Dose Groups

- The study agent is extended-release metformin.

- ER metformin 500 mg per day (1 tablet QD) for 1 week, then 1,000mg per day (2 tablets QD) for the second week, then 2,000 mg (2 tablets BID) for the remaining treatment period.
- Duration of treatment is 12-14 weeks.

5.2 Study Agent Administration

- For the first week 1 tablet will be taken QD with evening meal, then for the second week 2 tablets will be taken QD with evening meal, and for the remaining weeks 2 tablets will be taken BID with morning and evening meals.
- Tablets should be swallowed whole and never crushed or chewed.

5.3 Run-in Procedures

Not applicable.

5.4 Contraindications

Metformin is contraindicated in patients with

- Renal disease or renal dysfunction. Metformin will be discontinued for $eGFR \leq 30$ mL/min.
- Known hypersensitivity to metformin hydrochloride
- Acute or chronic metabolic acidosis
- Iodinated contrast media, intravascular use in radiologic studies; possible acute alteration of renal function resulting in increased risk of lactic acidosis
- Hepatic impairment, as defined in the exclusion criteria

If a subject requires a radiologic exam involving intravascular administration of iodinated contrast materials while participating in the study, she/he must discontinue study agent for at least 48 hours prior to having the exam and will not be permitted to restart study medication until at least 48 hours following the procedure and only after renal function has been re-evaluated and found to be normal.

5.5 Concomitant Medications

Participants may not use non-study metformin or other biguanides while on study.

Cationic drugs (e.g., amiloride, digoxin, morphine, procainamide, quinidine, quinine, ranitidine, triamterene, trimethoprim, or vancomycin) that are eliminated by renal tubular secretion theoretically have the potential for interaction with metformin by competing for common renal tubular transport systems. Careful patient monitoring is recommended in patients who are taking cationic medications that are excreted via the proximal renal tubular secretory system.

All medications (prescription and over-the-counter), vitamin and mineral supplements, and/or herbs taken by the participant will be documented on the concomitant medication CRF and will include: 1) start and stop date, dose and route of administration, and indication. Medications taken for a procedure (e.g., biopsy) should also be included.

5.6 Dose Modification

The CTCAE version 4 will be used for toxicity reporting.

Dose reductions will be made only if the toxicities are possibly, probably, or definitely related to the study drug. For adverse events not related or unlikely to be related to study drug, the dose may be suspended at the discretion of the investigator.

Grade 1 toxicity or less, no dose modification will be made unless the adverse event is unacceptable to the physician or participant.

Grade 2 toxicity, dosage will be reduced by 500 mg (current dose level minus 500 mg). For second appearance of grade 2 toxicity, therapy will be discontinued until toxicity resolves to grade 1 or less not to exceed a 4 week period. At that time, the use of study drug will be resumed with the dosage further reduced by 500 mg. For third appearance of grade 2 toxicity, participants will be taken off study.

Grade 3 toxicity possibly related to drug, therapy will be discontinued until toxicity resolves to grade 1 or less not to exceed a 4 week period. At that time, the use of study drug will be resumed with the dosage reduced by 500 mg. For grade 3 toxicity definitely or probably related to drug, participants will be taken off study. For second appearance of grade 3 toxicity, participants will be taken off study.

Each toxicity will be evaluated according to the grade at presentation, even if the same toxicity presents with a different prior grade. If a participant experiences a grade 2 toxicity followed by a grade 3 toxicity, the dose will be discontinued until toxicity resolves to grade 1 or less not to exceed a 4 week period. For a third episode of either grade 2 or 3 toxicities the drug will be discontinued. Conversely, if a participant has a grade 3 toxicity followed by a grade 2 toxicity with the appropriate changes to drug dose, a third appearance of either a grade 2 or grade 3 toxicity will lead to discontinuation of the study drug. Grade 4 toxicity, participants will be taken off study.

The participant will come off study if the drug cannot be restarted in 4 weeks (cumulative throughout duration of study) for any of the toxicities.

The participant will come off study for $eGFR \leq 30$ mL/min.

The study site principal investigator will be notified immediately of any grade 3 or 4 adverse events. The study investigators will decide if the adverse event is related to the agent.

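### Section 5.6 gives two different actions for a probably or definitely drug-related grade 3 toxicity that follows a grade 2, and does not say which one prevails

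*Combined protocol and SAP*

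**What the plan says.** All the operative text is in section 5.6.

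- **Grade 3 paragraph, possibly related.** "Grade 3 toxicity possibly related to drug, therapy will be discontinued until toxicity resolves to grade 1 or less", with a 4-week limit on the hold. Then: "At that time, the use of study drug will be resumed with the dosage reduced by 500 mg".
- **Grade 3 paragraph, probably or definitely related.** "For grade 3 toxicity definitely or probably related to drug, participants will be taken off study". Nothing here depends on what happened before.
- **Mixed-grade paragraph.** It opens with "Each toxicity will be evaluated according to the grade at presentation, even if the same toxicity presents with a different prior grade". It then says "If a participant experiences a grade 2 toxicity followed by a grade 3 toxicity, the dose will be discontinued until toxicity resolves". The hold ends at grade 1 or lower and again may last at most 4 weeks. This sequence sentence mentions neither attribution nor a restart dose. The next sentence is "For a third episode of either grade 2 or 3 toxicities the drug will be discontinued". The reverse order is covered by a sentence beginning "Conversely, if a participant has a grade 3 toxicity followed by a grade 2 toxicity with the appropriate changes to drug dose", which also stops drug at a third event.

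Section 11.1.4 defines five attribution levels. Section 5.6 treats the top three (possible, probable, definite) as drug-related for dose reductions. Sections 8.3 and 8.4 list reasons for stopping agent or leaving the study, and adverse events appear in both lists. Neither section refers to the grade 2 then grade 3 sequence.

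**The concern.** The sequence sentence is triggered by the order of grades alone, so it covers grade 3 events of every attribution. Because drug is stopped for good only at a third episode, it implies that the participant restarts after the second. For a probably or definitely related grade 3 event, the preceding paragraph says the opposite.

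What is at stake is participant safety and uniform handling across the three study sites. A coordinator could reasonably treat the sequence sentence as controlling, since it comes later and fits the participant's history more closely. That site could then give metformin again after a severe event judged probably or definitely due to metformin, which the grade 3 paragraph forbids.

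**Working it through.** Section 5.6 contains no statistical figure to reproduce. The check sets the rules side by side and then follows the dose.

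**Step 1. Action for a first grade 3 toxicity after a grade 2, by attribution**

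| Attribution of the grade 3 event | Grade 3 paragraph | Sequence sentence | Result |
|---|---|---|---|
| Possible | Hold up to 4 weeks, restart 500 mg lower | Hold up to 4 weeks, restart dose not stated | Same action |
| Probable | Off study | Hold up to 4 weeks | Conflict |
| Definite | Off study | Hold up to 4 weeks | Conflict |

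The rules conflict at 2 of 3 drug-related levels.

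**Step 2. Dose path from the full dose**

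- Full dose (section 5.1): 2,000 mg/day.
- After a first related grade 2 (section 5.6, reduce by 500 mg): 2,000 − 500 = 1,500 mg/day.
- Then a possibly related grade 3, under the grade 3 paragraph: hold, then 1,500 − 500 = 1,000 mg/day.
- Then a probably or definitely related grade 3:
  - grade 3 paragraph: off study, 0 mg/day;
  - sequence sentence with the 500 mg reduction carried over: hold, then 1,500 − 500 = 1,000 mg/day;
  - sequence sentence as written, with no reduction stated: hold, then 1,500 mg/day.

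**Step 3. Search for a tie-breaker**

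The nearest candidate is the sentence on grade at presentation. It says which grade to use. It does not mention attribution, and it does not say that the grade 3 paragraph overrides the sentence that comes straight after it. Sections 8.3 and 8.4 do not rank the two rules either.

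**Step 4. Frequency**

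The plan expects 26 participants to start the agent (section 13.3). Section 6.2 reports adverse event percentages for metformin but gives no grade 3 rate. The expected number of affected participants cannot be calculated from the documents.

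**The case against.** The strongest reply is that the paragraph resolves itself when read as a whole. If each toxicity is judged by its grade at presentation, a grade 3 after a grade 2 is a grade 3, and it returns to the grade 3 paragraph, which already sorts by attribution. The sequence sentence repeats the hold wording of the possibly related rule. It contains no express instruction to restart. Its mirror image, on grade 3 followed by grade 2, makes sense only for participants still on drug after a grade 3, that is, those whose event was possibly related. On this view the mixed-grade paragraph merely counts episodes and presupposes the attribution rules above it.

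That reading is plausible and is probably what was intended. It remains an inference from several clues. The authors wrote the possibly related limit into the grade 3 paragraph and left it out of the sequence sentence. A restart is not ordered, but deferring discontinuation to a third episode implies one.

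Two further replies have weight. First, both readings stop drug at once, and neither allows it back before the event resolves to grade 1 or less. Second, there is oversight: "The study site principal investigator will be notified immediately of any grade 3 or 4 adverse events", and section 12.4 provides for monthly Consortium review of adverse events and DSMB safety oversight. These make an unnoticed restart less likely, but they do not tell the site which rule to apply. It is also fair to say that 2 of 3 counts attribution labels, not participants or risk, and that the defect is one of wording, since nobody disputes the off-study policy itself.

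**Conclusion.** The concern holds. Section 5.6 prescribes both removal from study and a hold of up to 4 weeks for the same event, without saying which prevails. The conflict is confined to grade 3 events judged probably or definitely related that follow a grade 2. It does not arise for possibly related events, although the sequence sentence leaves their restart dose to be found elsewhere.

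The conclusion rests on reading the sequence sentence as written, with no implied attribution limit. If the sponsor confirms that the limit was intended, the policy is sound and only the text needs correcting. No effect on the endpoint, analysis, sample size or power is claimed. The change should be made because the ambiguity lies in a stopping rule for severe drug-related toxicity.

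**What to change.** Replace the sentence on grade 2 followed by grade 3 with wording to this effect:

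> When a grade 3 toxicity judged possibly related comes after a grade 2, hold drug until the event is grade 1 or lower, for no more than 4 weeks, then restart at 500 mg below the current dose. A grade 3 toxicity judged probably or definitely related ends study participation as stated above, whatever grade came before it.

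Everything else in section 5.6 stays as it is. The conflict falls from 2 of 3 attribution levels to 0 of 3, and the restart dose is stated.

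The cost is one sentence, built from the off-study rule and the 500 mg reduction already in the section. Under section 14.3 it needs an amendment approved by DCP and then by the IRB, and it can be bundled with the next one. It adds no procedures, visits or participants.

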5.7 Adherence/Compliance

5.7.1 Participants will be considered compliant for secondary “per protocol” statistical analysis if they have taken $\geq 80\%$ of their assigned study doses based on capsule count.

5.7.2 The primary measure of compliance is pill count. The secondary measure of compliance will be the Intake Calendar. Serum levels of study agent will also be used to confirm compliance.

6. PHARMACEUTICAL INFORMATION

6.1 Metformin (IND exempt)

Metformin is an oral drug approved in the US for the management of hyperglycemia in type 2 diabetes mellitus (T2DM) in conjunction with diet and exercise [33, 34]. It is also commonly used off-label for polycystic ovary syndrome in women. Its major mechanism of action is the suppression of hepatic gluconeogenesis which reduces serum glucose and secondarily reduces insulin levels [35]. Compelling evidence demonstrates that in a variety of human cancer cell lines and animal models, metformin treatment

reduces tumor cell growth in part by reducing mTORC1 activity [12-15]. On the molecular level, metformin is believed to inhibit mitochondrial electron transfer from complex I to II, thereby resulting in lower cellular ratio of ATP/ADP levels which can secondarily activate adenosine monophosphate kinase (AMPK) via the tumor suppressor liver kinase B1[36]. Additional activities of metformin also include activation of muscular glucose uptake transporters [37, 38] and repression of glucagon receptor adenylate cyclase activation [39, 40].

The drug product, metformin ER tablet (NDC 62037-0571-01; Actavis [Parsippany, NJ], formerly Watson Laboratories [Corona, CA]) (<http://www.medicationdaily.com/metformin-hydrochloride/ndc/62037-0571-01>) contains 500 mg metformin HCl and the following inactive ingredients: hypromellose 2208, colloidal silicon dioxide, and magnesium stearate. The tablet comprises a monohydrophilic polymer matrix system in which metformin HCl is combined with a drug release controlling polymer to form the matrix. After administration, fluid from the gastrointestinal (GI) tract enters the tablet, causing the polymers to hydrate and swell. Drug is released slowly from the dosage form by a process of diffusion through the gel matrix that is essentially independent of pH. The hydrated polymer system is not rigid and is expected to be broken up by normal peristalsis in the GI tract. The biologically inert components of the tablet may occasionally remain intact during GI transit and will be eliminated in the feces as a soft, hydrated mass.

6.2 Reported Adverse Events and Potential Risks

Metformin is considered to have a benign safety profile [41, 42]. According to the US prescribing information (PI) for metformin HCl ER (NDC 62037-0571-01), common adverse events (AEs) for metformin ER *vs.* placebo were diarrhea (9.6% *vs.* 2.6%) and nausea/vomiting (6.5% *vs.* 1.5%) (<http://www.medicationdaily.com/metformin-hydrochloride/ndc/62037-0571-01>). In a clinical study of immediate-release (IR) metformin *vs.* placebo in patients with T2DM, GI symptoms such as diarrhea (53.2% *vs.* 11.7% placebo), nausea and vomiting (25.5% *vs.* 8.3% placebo), abdominal discomfort (6.4% *vs.* 4.8% placebo), flatulence (12.1% *vs.* 5.5% placebo), indigestion (7.1% *vs.* 4.1% placebo), and asthenia (9.2% *vs.* 5.5% placebo) were the most common reactions to the drug. These symptoms were dose-dependent, transient, and resolved spontaneously with continued use. Diarrhea led to discontinuation of medication in 6% of subjects treated with metformin. Additional adverse reactions reported in 1 to 5% of subjects receiving active drug, and more commonly reported than in the placebo group, include abnormal stools, hypoglycemia, myalgia, lightheaded, dyspnea, nail disorder, rash, increased sweating, taste disorder, chest discomfort, chills, flu syndrome, flushing and palpitation.

A recently published multicenter, randomized, placebo-controlled trial in patients with type 2 diabetes reported on vitamin B₁₂ deficiency with long-term metformin treatment. Compared with placebo, metformin treatment was associated with a mean decrease in vitamin B₁₂ concentration of ~19% (95% confidence interval (CI) -24% to -14%; *p*<0.001). The absolute risk of vitamin B₁₂ deficiency (<150 pM) at study end was 7.2 percentage points higher in the metformin group than in the placebo group (95% CI 2.3 to 12.1; *p*=0.004) [43].

According to the metformin HCl ER PI, lactic acidosis is a rare, but serious, metabolic complication that can occur due to metformin accumulation during treatment with metformin. When it occurs, it is fatal in approximately 50% of the cases. Lactic acidosis may also occur in association with a number of pathophysiologic conditions, including diabetes mellitus, and whenever there is significant tissue hypoperfusion and hypoxemia. Lactic acidosis is characterized by elevated blood lactate levels (>5 mM), decreased blood pH, electrolyte disturbances with an increased anion gap, and an increased lactate/pyruvate ratio. Metformin plasma levels >5 µg/mL are generally found when the drug is implicated as the cause of lactic acidosis.

The incidence of lactic acidosis in patients receiving metformin is very low (~0.03 cases/1000 patient-years, with ~0.015 fatal cases/1000 patient-years). In more than 20,000 patient-years of exposure to metformin in

clinical trials, there were no reports of lactic acidosis. Reported cases have occurred primarily in diabetic patients with significant renal insufficiency, including both intrinsic renal disease and renal hypoperfusion, often in those with multiple concomitant medical/surgical problems and who take multiple concomitant medications. Patients with congestive heart failure require pharmacologic management, in particular those with unstable or acute congestive heart failure who are at risk of hypoperfusion and hypoxemia, are at increased risk of lactic acidosis. The risk of lactic acidosis increases with the degree of renal dysfunction and with patient age. Drug should be withheld in the presence of any condition associated with hypoxemia, dehydration, or sepsis. Because impaired hepatic function can significantly impair the ability to clear lactate, metformin should generally be avoided in patients with clinical or laboratory evidence of hepatic disease. Alcohol can potentiate the effects of metformin on lactate metabolism. Drug treatment should be temporarily discontinued prior to any intravascular radiocontrast study and for any surgical procedure [44, 45].

In support of the previously reported low risk of lactic acidosis, a recently published systematic review assessed the risk of lactic acidosis with metformin use in type 2 diabetes mellitus. Pooled data from 347 comparative trials and cohort studies revealed no cases of lactic acidosis in 70,490 patient-years of metformin use. The authors concluded that there was no evidence from prospective comparative trials or from observational cohort studies that metformin is associated with an increased risk of lactic acidosis compared to other antihyperglycemic treatments [46, 47].

Unlike sulfonylureas, metformin does not produce hypoglycemia in either T2DM patients or normal subjects, and does not cause hyperinsulinemia. Non-diabetic patients with polycystic ovary syndrome have been safely treated with a hypocaloric diet in combination with oral metformin 850 mg twice daily for a duration of 12 months [48, 49].

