⁶ Telephone (or email) contact within 3 days of starting the agent and before and after each dose escalation. Participants are eligible for dose escalation only in the absence of grade 2 or higher toxicities.

⁷ CMP includes serum glucose, urea nitrogen, creatinine, sodium, potassium, chloride, bicarbonate, total protein, albumin, calcium, alkaline phosphatase, ALT, AST, total bilirubin. Calculations included with the CMP are: BUN/creatinine ratio, anion, gap, globulin, alb/glob ratio, eGFR.

⁸ Physical exam includes assessment of chest, heart, abdomen, and lower extremities for pedal edema.

⁹ Telephone (or email) contact at Week 9 (± 3 days).

¹⁰ Saliva should be collected between 8 am and 12 noon, if feasible.

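### For a first drug-related grade 2 dehydration, section 5.6 prescribes a 500 mg reduction where section 6.2 says to withhold metformin, and no operative section requires the hold

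*Combined protocol and SAP*

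**What the plan says.** Section 6.2, in its lactic acidosis account taken from the prescribing information, states: "Drug should be withheld in the presence of any condition associated with hypoxemia, dehydration, or sepsis". The same paragraph asks for interruption around intravascular contrast studies and surgery.

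Section 5.6 sets the dosing response by grade, for toxicities at least possibly related to the drug:

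- Grade 1 or below: "Grade 1 toxicity or less, no dose modification will be made unless the adverse event is unacceptable to the physician or participant".
- First grade 2: "Grade 2 toxicity, dosage will be reduced by 500 mg (current dose level minus 500 mg". No hold is ordered.
- Second grade 2: stop until the event is back to grade 1 or lower, for at most 4 weeks, then resume at a further 500 mg less.
- Grade 3: hold if possibly related; off study if probably or definitely related.
- Grade 4: off study.

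For events judged unrelated or unlikely to be related, 5.6 leaves suspension to the investigator.

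Section 5 opens with a pointer: "Reported adverse events (AEs) and potential risks are described in Section 6.2". Section 5.4 makes the contrast hold mandatory, with restart "only after renal function has been re-evaluated and found to be normal", and lists hepatic impairment as a contraindication. It does not mention dehydration, hypoxemia or sepsis. Section 8.3 lists adverse events and medical contraindications among the reasons for which a participant may stop the agent.

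**The concern.** A site that looks up the response to a first related grade 2 event finds a reduction in 5.6, and finds a hold only at the next step. If the event is dehydration, the protocol's own risk text asks for a hold now. Nothing in the documents says how the two fit together.

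The setting is plausible. Section 6.2 gives diarrhea at 9.6% against 2.6% on placebo and nausea or vomiting at 6.5% against 1.5% for the extended-release product, and the trial reaches 2,000 mg/day after two weeks. Entry is allowed at an eGFR above "40 mL/min using the Cockcroft-Gault equation", and 6.2 says the lactic acidosis risk rises with renal dysfunction. Creatinine is scheduled only at baseline and at weeks 12-14 (section 7.1), so the stop at eGFR 30 mL/min or below has no scheduled laboratory trigger during treatment.

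The escalation check in 7.1 ("Participants are eligible for dose escalation only in the absence of grade 2 or higher toxicities") helps in weeks 1 and 2. From week 3 no escalation remains, so it changes nothing there.

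**Working it through.** **1. Dose under each text.** Inputs: the dose steps in 5.1 (500, 1,000, then 2,000 mg/day), the 5.6 rules, and the 6.2 sentence.

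| Situation (dehydration) | Under 5.6 | Under 6.2 | Different? |
|---|---|---|---|
| First related grade 2, week 1 | 500 - 500 = 0 mg/day | 0 | No |
| First related grade 2, week 2 | 1,000 - 500 = 500 mg/day (50%) | 0 | Yes |
| First related grade 2, week 3 on | 2,000 - 500 = 1,500 mg/day (75%, 3 tablets) | 0 | Yes |
| Second related grade 2 | Hold | 0 | No |
| Related grade 3 | Hold or off study | 0 | No |
| Grade 4 | Off study | 0 | No |
| Unrelated event | Investigator may suspend | 0 | Compatible, but hold not required |

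Grade 1 resembles the last row: the default is no change, but the physician may act.

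**2. When it can arise.** From day 8 to the end of dosing: 84 - 7 = 77 of 84 days (91.7%) for 12 weeks, or 98 - 7 = 91 of 98 days (92.9%) for 14 weeks. This is a calendar window, not a probability. The documents give no rate of grade 2 dehydration, so the frequency cannot be derived. For scale only, the gastrointestinal rates in 6.2 applied to 26 participants give 26 x 0.096 = 2.5 people with diarrhea and 26 x 0.065 = 1.7 with nausea or vomiting, with no grade stated.

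**3. Expected lactic acidosis.**

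- Exposure: 26 x 12/52 = 6.0 to 26 x 14/52 = 7.0 patient-years.
- At the 0.03 per 1,000 patient-years in 6.2: 0.00018 to 0.00021 cases.
- Fatal, at 0.015 per 1,000: 0.00009 to 0.000105.
- The pooled review in 6.2 found 0 cases in 70,490 patient-years. One-sided 95% upper limit: -ln(0.05)/70,490 = 0.0425 per 1,000, or 0.00025 to 0.00030 cases here.

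These are average rates, not rates given dehydration.

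**4. Cost of a hold in adherence.** Tablets assigned: 7 + 14 + 280 = 301 over 12 weeks, or 7 + 14 + 336 = 357 over 14 weeks. An assumed 7-day hold at full dose omits 7 x 4 = 28 tablets: 28/301 = 9.3% or 28/357 = 7.8%. Section 5.7 counts a participant as compliant at 80% or more "of their assigned study doses based on capsule count". One such hold on its own stays within the 20% allowed if held doses count as assigned, and costs nothing if they do not.

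**The case against.** The strongest reply is that the two texts do not compete. Section 6.2 is pharmaceutical information drawn from the prescribing information, and its verb is advisory; 5.6 is the operative rule. Section 5.6 also sets a dose level and never says that dosing must run without a break, so a site can hold during dehydration and then resume at 1,500 mg/day, obeying both. Section 8.3 permits stopping. Section 11 refers sites to 6.2 and to the package insert, and 14.2.6 requires a signed brochure or package insert acknowledgement. Most of this stands. A reader might infer that the protocol orders continued dosing in dehydrated participants; the documents do not support that, because continuation is only implied by a reduction being ordered where the next step orders a stop.

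The case is also narrow. If second appearances are counted across toxicities, as the third-episode wording in 5.6 suggests, dehydration after an earlier grade 2 diarrhea is already held. Section 4.2 excludes renal disease, liver disease, drug-treated diabetes, symptomatic heart failure and heavy drinking, which removes many of those at highest risk.

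What does not stand is that 6.2 is only background. Section 5.4 turned the contrast precaution from the same paragraph into a mandatory hold. Dehydration received no such rule, so a permitted hold is all that remains. Section 5.6 writes in discretion for unrelated events and for grade 1, but none for a related grade 2 event.

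**Conclusion.** This is a minor safety inconsistency and a cheap improvement, of low severity. For drug-related dehydration that is a participant's first grade 2 toxicity, from week 2 on, 5.6 prescribes only a reduction to 1,500 mg/day (500 mg/day in week 2) while 6.2 asks for a hold that no operative section requires.

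The expected harm is about 0.0002 lactic acidosis cases over the whole trial. That figure assumes all 26 participants complete dosing and that the average rate applies; the risk given dehydration is not in the documents and may be higher. The scenario also assumes that an investigator grades the dehydration as 2 and attributes it to the drug.

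Two wider readings should be resisted. A reader might extend the conflict to unrelated sepsis or hypoxemia, or to surgery. There the operative sections leave the hold to discretion or say nothing, so they do not oppose 6.2. A reader might also suspect an effect on efficacy results. There is none: the endpoints are unchanged, and 13.8 assesses all participants with endpoint data.

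**What to change.** Insert in 5.6, ahead of the grade-based rules:

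*Regardless of grade or attribution, study agent is withheld during dehydration, hypoxemia or sepsis (see 6.2) and resumed once the condition has resolved, at any reduced dose due under the grade-based rules. The existing eGFR ≤30 mL/min stop, off-study rules and 4-week limit are unchanged.*

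Add a matching bullet to 5.4. Hypoxemia and sepsis are included because they stand in the same 6.2 sentence.

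Nothing more is needed. A restart threshold at the entry eGFR of above 40 mL/min would clash with the stop at 30 or below: a participant at 35 could keep dosing under 5.6 but could not restart after a hold. A mandatory creatinine recheck, a surgery clause, or an exemption of unrelated holds from the 4-week limit would each go beyond the inconsistency.

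The cost is one sentence pair, one bullet and a few short dose interruptions.
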